10.7. Appendix 7: Kidney Safety: Monitoring Guidelines

10.7.1. Laboratory Assessment of Change in Kidney Function and Detection of Kidney Injury

Standard kidney safety monitoring requires assessment of baseline and postbaseline Screat measurement to estimate kidney function [eg, Screat-based eGFR]. Obtaining Screening or Baseline Scys and postbaseline reflex Scys (if confirmed Screat increase ≥0.3 mg/dL) makes it feasible to distinguish AKI from DICI. If Screat increase is confirmed after baseline, then reflex measurement of Scys is indicated:

ADULTS: Currently, 2021 CKD-EPI eGFR equations (Screat only-based and combined Screat plus Scys-based) are valid for use in adults only. At baseline Screat and Scys values are needed to calculate 2021 CKD-EPI eGFR by Screat only-based equation (see Section 10.7.2.1) and by combined Screat plus Scys-based equation. When post-baseline Screat increase ≥0.3 mg/dL is confirmed, then reflex Scys measurement is needed to enable post-baseline comparison of eGFR changes (Screat only-based eGFR and combined Screat plus Scys eGFR).

10.7.2. Age-Specific Kidney Function Calculation Recommendations

10.7.2.1. Adults (18 Years and Above)—2021 CKD-EPI Equations

eGFR (mL/min/1.73m²)[17]

2021 CKD- EPI Screat Only	Screat (mg/dL)	Scys (mg/L)	Recommended eGFR Equation
Female	if ≤ 0.7	NA	$eGFR = 143 \times (Screat/0.7)^{-0.241} \times (0.9938)^{Age}$
Female	if > 0.7	NA	$eGFR = 143 \times (Screat/0.7)^{-1.200} \times (0.9938)^{Age}$
Male	if ≤ 0.9	NA	$eGFR = 142 \times (Screat/0.9)^{-0.302} \times (0.9938)^{Age}$
Male	if > 0.9	NA	$eGFR = 142 \times (Screat/0.9)^{-1.200} \times (0.9938)^{Age}$
2021 CKD-	Screat	Scys	Recommended eGFR Equation
EPI	(mg/dL)	(mg/L)	
Screat-Scys Combined			
Female	if ≤ 0.7	if ≤ 0.8	$eGFR = 130 \times (Screat/0.7)^{-0.219} \times (Scys/0.8)^{-0.323} \times (0.9961)^{Age}$
Female	if ≤ 0.7	if > 0.8	$eGFR = 130 \times (Screat/0.7)^{-0.219} \times (Scys/0.8)^{-0.778} \times (0.9961)^{Age}$
Female	if > 0.7	if ≤ 0.8	$eGFR = 130 \times (Screat/0.7)^{-0.544} \times (Scys/0.8)^{-0.323} \times (0.9961)^{Age}$
Female	if > 0.7	if > 0.8	$eGFR = 130 \times (Screat/0.7)^{-0.544} \times (Scys/0.8)^{-0.778} \times (0.9961)^{Age}$
Male	if ≤ 0.9	if ≤ 0.8	$eGFR = 135 \times (Screat/0.9)^{-0.144} \times (Scys/0.8)^{-0.323} \times (0.9961)^{Age}$
Male	if ≤ 0.9	if > 0.8	$eGFR = 135 \times (Screat/0.9)^{-0.144} \times (Scys/0.8)^{-0.778} \times (0.9961)^{Age}$
Male	if > 0.9	if ≤ 0.8	eGFR = $135 \times (\text{Screat}/0.9)^{-0.544} \times (\text{Scys}/0.8)^{-0.323} \times (0.9961)^{\text{Age}}$
Male	if > 0.9	if > 0.8	eGFR = $135 \times (\text{Screat}/0.9)^{-0.544} \times (\text{Scys}/0.8)^{-0.778} \times (0.9961)^{\text{Age}}$

10.7.3. Kidney Function Calculation Tools

The sponsor has provided the following resources to investigational sites when required to calculate age-specific kidney function at Screening, Baseline, and post-Baseline visits. Site calculations of kidney function can be performed manually, using the age appropriate formulae (see Section 10.7.2) and can use recommended online kidney function calculators to reduce the likelihood of a calculation error.

The United States National Kidney Foundation Online Calculators.

• Adults (18 years and above) - 2021 CKD-EPI Creatinine Online Calculator (eGFR): https://www.kidney.org/professionals/KDOQI/gfr calculator

Investigational sites are responsible to ensure that the accurate age-specific equation is selected and that the correct units for serum creatinine (mg/dL only), serum cystatin C (mg/L only), total body weight (kg only), and age (years). Investigators are expected to (i) review and confirm correctness of the kidney function calculation results and (ii) evaluate the calculated value within the context of historical information available to them in the participant's medical record. Investigators are responsible for the clinical oversight of the participant eligibility process, kidney function calculation, and dose selection and adjustments per study protocol. Investigators are encouraged to direct questions or uncertainties regarding kidney function and dosing to the Pfizer Clinical Team and Medical Monitor, if needed.

10.7.4. Adverse Event Grading for Kidney Safety Laboratory Abnormalities

AE grading for decline in kidney function will be according to CTCAE criteria.

CTCAE Term (2017)	Grade 1	Grade 2	Grade 3	Grade 4	Grade 5
AKI	NA	NA	Hospitalization indicated	Life-threatening consequences; dialysis indicated	Death
classified as p				cs) and is traditionally r post-renal causes (ure	teral or
Creatinine increased	>ULN to 1.5 × ULN	>1.5 to 3.0 × baseline OR >1.5 to 3.0 × ULN	>3.0 to 6.0 × baseline OR >3.0 to 6.0 × ULN	>6.0 × ULN	NA
CKD	eGFR ≥60 to 89 mL/min/1.73m ² OR eCrCl ≥60 to 80 mL/min	eGFR 30 to 59 mL/min/1.73m ² OR eCrCl 30 to 59 mL/min	eGFR 15 to 29 mL/min/1.73m ² OR eCrCl 15 to 29 mL/min	eGFR <15 mL/min/1.73m² OR eCrCl <15 mL/min OR dialysis indicated	Death
Proteinuria	ADULTS: Proteinuria 1+ OR Proteinuria >0.5 to <1.0 g/24 h	ADULTS: Proteinuria 2+ or 3+ OR Proteinuria 1.0 to <3.5 g/24 h	ADULTS: Proteinuria 4+ OR Proteinuria ≥3.5 g/24 h	NA	NA

CKD: A disorder characterized by gradual and usually permanent loss of kidney function resulting in kidney failure.

10.8. Appendix 8: ECG Findings of Potential Clinical Concern

ECG Findings That May Qualify as AEs

- Marked sinus bradycardia (rate <40 bpm) lasting minutes.
- New PR interval prolongation >280 ms.
- New prolongation of QTcF to >480 ms (absolute).
- New prolongation of QTcF by >60 ms from baseline.
- New-onset atrial flutter or fibrillation, with controlled ventricular response rate: ie, rate <120 bpm.
- New-onset type I second-degree (Wenckebach) AV block of >30-second duration.
- Frequent PVCs, triplets, or short intervals (<30 seconds) of consecutive ventricular complexes.

ECG Findings That May Qualify as SAEs

- QTcF prolongation >500 ms.
- Absolute value of QTcF > 450 ms AND QTcF change from baseline >60 ms.
- New ST-T changes suggestive of myocardial ischemia.
- New-onset LBBB (QRS complex>120 ms).
- New-onset right bundle branch block (QRS complex>120 ms).
- Symptomatic bradycardia.
- Asystole
 - In awake, symptom-free participants in sinus rhythm, with documented asystolic pauses ≥3 seconds or any escape rate <40 bpm, or with an escape rhythm that is below the AV node;
 - In awake, symptom-free participants with atrial fibrillation and bradycardia with 1 or more asystolic pauses of at least 5 seconds or longer.
- Atrial flutter or fibrillation, with rapid ventricular response rate: rapid = rate >120 bpm.

- Sustained supraventricular tachycardia (rate >120 bpm) ("sustained" = short duration with relevant symptoms or lasting >1 minute).
- Ventricular rhythms >30 seconds' duration, including idioventricular rhythm (HR <40 bpm), accelerated idioventricular rhythm (HR >40 bpm to <100 bpm), and monomorphic/polymorphic ventricular tachycardia (HR >100 bpm [such as torsades de pointes]).
- Type II second-degree (Mobitz II) AV block.
- Complete (third-degree) heart block.

ECG Findings That Qualify as SAEs

- Change in pattern suggestive of new myocardial infarction.
- Sustained ventricular tachyarrhythmias (>30-seconds duration).
- Second- or third-degree AV block requiring pacemaker placement.
- Asystolic pauses requiring pacemaker placement.
- Atrial flutter or fibrillation with rapid ventricular response requiring cardioversion.
- Ventricular fibrillation/flutter.
- At the discretion of the investigator, any arrhythmia classified as an adverse experience.

The major events of potential clinical concern listed above are recommended as "alerts" or notifications from the core ECG laboratory to the investigator and Pfizer study team, and not to be considered as all-inclusive of what is to reported as AEs/SAEs.

10.9. Appendix 9: Prohibited Concomitant Medications That May Result in DDI

The prohibited concomitant medications listed below should not be taken with PF-06954522 for the period of time at least equal to the required washout period listed in the table, and throughout the conduct of the study.

The Pfizer study team is to be notified of any prohibited medications taken during the study. After consulting with the sponsor, the investigator will make a judgment on the ongoing participation of any participant with prohibited medication use during the study.

This list of drugs prohibited for potential DDI concerns with the IMP may be revised during the course of the study with written notification from sponsor, to include or exclude specific drugs or drug categories for various reasons (eg, emerging DDI results for the IMP, availability of new information in literature on the DDI potential of other drugs), if the overall benefit:risk assessment is not impacted or if the changes do not significantly impact the safety of participants or the scientific value of the trial

This is not an all-inclusive list. Site staff should consult with the sponsor or designee with any questions regarding potential DDI.

Investigators should consult the product label for any other medication used during the study for information regarding medication that is prohibited for concomitant use.

10.10. Appendix 10: Abbreviations

The following is a list of abbreviations that may be used in the protocol.

Abbreviation	Term
A1 to A3	albuminuria (KDIGO albuminuria severity standardization)
Abs	absolute
ADL	activity/activities of daily living
AE	adverse event
AESI	adverse event of special interest
CCI	
AKI	acute kidney injury
ALT	alanine aminotransferase
ANOVA	analysis of variance
AST	aspartate aminotransferase
AUC	area under the concentration-time curve
AUC ₂₄	area under the concentration-time curve from time 0 to 24 hours
AUCinf	area under the concentration-time curve from time 0 to infinity
AUC _{inf} (dn)	dose-normalized AUC _{inf}
AUC _{last}	area under the concentration-time curve from 0 to time of last
	measurable concentration
AUC _{last} (dn)	dose-normalized AUC _{last}
AV	atrioventricular
AxMP	auxiliary medicinal product
BA	bioavailability
BBS	Biospecimen Banking System
CCI	
BE	bioequivalence
BMI	body mass index
BP	blood pressure
bpm	beats per minute
BUN	blood urea nitrogen
CCI	
C_{eff}	steady state efficacious concentration
CFR	Code of Federal Regulations
CIOMS	Council for International Organizations of Medical Sciences
CK	creatine kinase
CKD-EPI	Chronic Kidney Disease Epidemiology Collaboration
CL	total clearance of drug from eg, plasma
CL/F	apparent clearance of drug from eg, plasma
CL_p	plasma clearance
C _{max}	maximum observed concentration
C _{max} (dn)	dose-normalized C _{max}
CO_2	carbon dioxide (bicarbonate)
	Learban diavida (bicarbanata)

Abbreviation	Term
COVID-19	coronavirus disease 2019
CCI	
CRF	case report form
CRO	contract research organization
CRU	clinical research unit
CSR	Clinical Study Report
CT	clinical trial
CTCAE	Common Terminology Criteria for Adverse Events
CTIS	Clinical Trial Information System
CV	cardiovascular
CCI	
DCT	data collection tool
DDI	drug-drug interaction
DICI	drug-induced creatinine increase
DIKI	drug-induced kidney injury
DILI	drug-induced liver injury
DNA	deoxyribonucleic acid
DU	dispensable unit
EC	ethics committee
ECC	emergency contact card
ECG	electrocardiogram or electrocardiography
CCI	
eCrCl	estimated creatinine clearance
eCRF	electronic case report form
EDB	exposure during breastfeeding
E-DMC	External Data Monitoring Committee
EDP	exposure during pregnancy
EDR	extemporaneous dispensing record
eGFR	estimated glomerular filtration rate
EGFR	epidermal growth factor receptor
eICD	electronic informed consent document
EMA	European Medicines Agency
ET	end of treatment
eSAE	electronic serious adverse event
ESR	erythrocyte sedimentation rate
EU	European Union
EudraCT	European Union Drug Regulating Authorities Clinical Trials
	(European Clinical Trials Database)
FDA	Food and Drug Administration
FIH	first in human
FSH CCI	follicle-stimulating hormone
F/U	follow-up

Abbreviation	Term
G1 to G5	Grade (KDIGO eGFR category standardization)
GCP	Good Clinical Practice
GGT	gamma-glutamyl transferase
GLP-1	glucagon-like peptide-1
GLP-1R	glucagon-like peptide-1 receptor
GLP-1RA	glucagon-like peptide-1 receptor agonist
HbA1c	glycated hemoglobin
HBcAb	hepatitis B core antibody
HBsAb	hepatitis B surface antibody
HBsAg	hepatitis B surface antigen
HCVAb	hepatitis C antibody
HIV	human immunodeficiency virus
HR	heart rate
HRT	hormone replacement therapy
IB	Investigator's Brochure
ICD	informed consent document
ICH	International Council for Harmonisation of Technical
	Requirements for Pharmaceuticals for Human Use
ID	identification
IMP	investigational medicinal product
IND	Investigational New Drug
INR	international normalized ratio
IPAL	Investigational Product Accountability Log
CCI	
IPM	investigational product manual
IQMP	integrated quality management plan
IRB	Institutional Review Board
IRC	internal review committee
IRT	Interactive Response Technology
ISO	International Organization for Standardization
IV	Intravenous(ly)
IWR	Interactive Web Response
K	Proportionality constant for Schwartz Equations (kidney function)
K ₂ EDTA	dipotassium ethylenediaminetetraacetic acid
k _{el}	first-order elimination rate constant
KDIGO	Kidney Disease Improving Global Outcomes
LBBB	left bundle branch block
LDH	lactate dehydrogenase
LFT	liver function test
LPD	local product document
CCI	1 1

Abbreviation	Term
MCH	mean corpuscular hemoglobin
MCHC	mean corpuscular hemoglobin concentration
MCV	mean corpuscular volume
MEN2	multiple endocrine neoplasia syndrome type 2
CCI	
MQI	medically qualified individual
MTC	medullary thyroid carcinoma
NA	not applicable
NHP	nonhuman primate
NIMP	noninvestigational medicinal product
NOAEL	no observed adverse effect level
CCI	
Pbo	placebo
CCI	
PCR	polymerase chain reaction
PCRU	Pfizer Clinical Research Unit
PD	pharmacodynamic(s)
PE	physical examination
CCI	
PGx	pharmacogenomic(s)
PI	principal investigator
PIB	powder in bottle
PK	pharmacokinetic(s)
PSSA	Pfizer's Serious Adverse Event Submission Assistant
PT	prothrombin time
PTA	post-trial access
PTH	parathormone
PVC	premature ventricular contraction/complex
QD	once daily
QTc	corrected QT interval
QTcF	QTc corrected using Fridericia's formula
QTL	quality tolerance limit
qual	qualitative
RBC	red blood cell
RNA	ribonucleic acid
SADE	serious adverse device effect
SAE	serious adverse event
SAP	Statistical Analysis Plan
SC	subcutaneous
SCL	supply chain lead
Scr	serum creatinine
Screat	serum creatinine

Abbreviation	Term
Scys	serum cystatin C
SoA	schedule of activities
SOP	standard operating procedure
SRSD	Single Reference Safety Document
SUSAR	Suspected Unexpected Serious Adverse Reaction
t _{1/2}	terminal phase half-life
T2DM	type 2 diabetes mellitus
T3	total triiodothyronine
T4	thyroxine
TB	tuberculosis
TBD	to be determined
T bili	total bilirubin
T _{max}	Time for C _{max}
THC	tetrahydrocannabinol
TOC	table of contents
TSH	thyroid-stimulating hormone
UACR	urine albumin/creatinine ratio
ULN CCI	upper limit of normal
CCI	
US	United States
USPI	United States Prescribing Information
UTI	urinary tract infection
V_{ss}	steady-state volume of distribution
V _z /F	apparent volume of distribution for extravascular dosing
WBC	white blood cell
WOCBP	woman/women of childbearing potential

#### 1. VERSION HISTORY

**Table 1. Summary of Changes** 

Version/ Date	Associated Protocol Amendment	Rationale	Specific Changes
1 14 Sept 2023	Original 17 July 2023	N/A	N/A

### 2. INTRODUCTION

This statistical analysis plan (SAP) provides the detailed methodology for summary and statistical analyses of the data collected in Study C4001001. This document may modify the plans outlined in the protocol; however, any major modifications of the primary endpoint definition or its analysis will also be reflected in a protocol amendment.

Text in *italics* is taken directly from the protocol.

# 2.1. Modifications to the Analysis Plan Described in the Protocol

No modifications.

# 2.2. Study Objectives, Endpoints, and Estimands

Type	Objective	Endpoint	Estimand
Primary:	-	-	
Safety (Section 3.1)	To evaluate the safety and tolerability of single oral doses of PF-06954522, administered to healthy adult participants.	Assessment of AEs, safety laboratory tests, vital signs (blood pressure, pulse rate, respiratory rate and temperature), cardiac telemetry and standard 12-lead ECGs, and PE.	N/A
Secondary:			•
PK (Section 3.2)	To characterize plasma PK of PF-06954522 following single oral doses of PF-06954522 administered to healthy adult participants.	PF-06954522 PK parameters: AUC last , C max , T max , and if data permit, AUC inf and t 1/2 .	N/A
Tertiary/Ex	cploratory:		
PK (Section 3.3.1)	To further characterize plasma PK of PF-06954522 following single oral doses of PF-06954522 administered to healthy adult participants.	Additional PF-06954522 PK parameters: $AUC_{last}(dn)$ , $C_{max}(dn)$ , and if data permit, $AUC_{inf}(dn)$ , $CL/F$ , and $V_z/F$ .	N/A
PK (Section 3.3.2)	Optional: to characterize the effect of food (high-fat breakfast) on the plasma PK of PF-06954522	PF-06954522 PK parameters after a high-fat meal: AUC last , C max , T max	N/A

	following single oral doses of PF- 06954522 in healthy adult participants.	and if data permit, $AUC_{inf}$ , $CL/F$ , $V_z/F$ and $t_{\frac{1}{2}}$ .	
CCI			N/A
Safety and PK (Section 3.3.4)	Optional: to explore the safety, tolerability, and plasma PK of PF-06954522 in healthy adult Japanese participants.	Assessment of AEs, safety laboratory tests, vital signs (blood pressure, pulse rate and temperature), standard 12-lead ECGs and the following PF-06954522 PK parameters in Japanese participants: AUC last , C max , T max , and if data permit, AUC inf , CL/F, V z /F and t ½ .	N/A

# 2.3. Study Design

This study is a randomized double-blinded (investigator- and participant-blinded), sponsor-open, first in human (FIH), single-ascending oral dose, 5-period crossover, placebo substitution design in 1 cohort of healthy adult participants. An additional optional cohort, enrolling healthy adult participants in up to 4 crossover periods, may be included to permit assessment of any of the following: repeat of a previously administered dose level; studying additional dose levels as dictated by the evaluated safety, tolerability or PK of earlier dose levels; or any other assessment needed to meet the objectives of this study. A second optional cohort enrolling Japanese participants to receive PF-06954522 or placebo in up to 3 periods, may be included.

Approximately 24 healthy adult participants will be enrolled in the study. This includes up to approximately 10 healthy participants for Cohort 1, up to approximately 8 healthy participants for optional Cohort 2 and up to approximately 6 healthy Japanese participants for the optional Cohort 3. The actual number of Japanese participants may be adjusted based on emerging data or operational factors with a maximum sample size of up to 8 participants (6 receiving PF-06954522 and 2 receiving placebo in each period).

A sample study design schematic is presented in Figure 1. It should be noted that this is for illustrative purposes, only.

Period 1 Period 2 Period 3 Period 4 Period 5 N=2Cohort 1 (n=10) ıı Âıı DER DER DER Telephone On-site N=2 ≥7d ≥7d ≥ 7d ≥ 7d follow-up follow-up N=2 visit visit N=2Period 1 Period 2 Period 3 Period 4 TBD TBD TBD Pbo ıııÂııı Optional DER DER DER TBD TBD Pbo TBD (n=8 Telephone screen On-site ≥7d ≥7d ≥ 7d follow-up TBD TBD follow-up Pbo TBD visit visit TBD TBD TBD Pbo Period 1 Period 2 Period 3 mÂm TBD TBD Pbo Optional On-site Telephone TBD TBD follow-up follow-up >7d TBD visit TBD Pbo visit

Figure 1. Study Design Schematic: Sequential, Placebo-Controlled, 5-Period, Crossover Design

- All doses in the schematic above (other than the starting dose of mg) are for illustrative purposes only, as treatment sequences, actual doses and dose increments may be adjusted during the study based on emerging safety, tolerability and PK data.
- Each period will consist of admission on Day -1, dosing on Day 1, and discharge on Day 4. There will be a washout interval of at least 7 days between consecutive doses administered to an individual participant. The washout interval may be adjusted based on data emerging from previous cohorts/periods.
- Dose escalation to occur following review of PK data through at least 24 hours post-dose and safety and tolerability data through at least 48 hours post-dose of the current period. Cumulative safety and tolerability data from all previous periods will also be reviewed.
- It is anticipated that the effect of food (dose administration with a high fat breakfast) on PF-06954522 PK
  will be assessed in the last Period of Cohort 1. This will be assessed at a dose level (to be chosen based on
  emerging data) that has been previously administered fasted within the same cohort. However, the effect of
  food may be assessed during any of the study periods/cohorts if thought necessary to achieve study objectives.
- On-site follow-up visit to occur 7-10 days after administration of the final dose of study intervention. Followup contact may occur via telephone contact and must occur 28-35 days after administration of the final dose of study intervention.
- DER: dose escalation review; Pbo: placebo; TBD: to be determined.

# 3. ENDPOINTS AND BASELINE VARIABLES: DEFINITIONS AND CONVENTIONS

# 3.1. Primary Endpoint(s)

Primary endpoints include assessment of adverse events (AEs), clinical safety laboratory tests, vital signs, cardiac telemetry, ECG parameters, and physical examinations during the entire study by dose, population and dietary allocation.

#### 3.1.1. Adverse Events

An AE is considered a TEAE if the event started during the effective duration of treatment. All events that start on or after the first dose of study intervention, but before the end of the study will be flagged as TEAEs. The algorithm will not consider any events that started prior to the first dose date.

Events that occur in a non-treatment period (eg, washout or follow-up) will be counted as treatment emergent and attributed to the most recent treatment taken.

A 3-tier approach for summarizing AEs will not be used due to the low number of participants planned to be recruited.

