6.6.1. Dose Escalation and Stopping Rules

Dose escalation stopping rules will be used to determine whether the maximal tolerated dose has been attained. Dose escalation may be stopped if it is determined that the limits of safety and/or tolerability have been reached. This decision will be made after a discussion takes place between the sponsor study team and the investigator. The sponsor study team may not overrule the investigator's decision to stop dose escalation. If dose escalation is stopped because of any of these criteria, additional cohorts may receive the same or lower doses of the study intervention.

The dose escalation will be terminated based on the following criteria:

- If 50% or more of the participants receiving active drug at a given dose level (but not
 participants receiving placebo) develop similar clinically significant laboratory, ECG,
 or vital sign abnormalities, in the same organ class, indicating dose-limiting
 intolerance.
- Severe nonserious AEs, considered as, at least, possibly related to study intervention administration, in 2 participants at a given dose level (but not participants receiving placebo), independent of within or not within the same system organ class, indicating dose-limiting intolerance.
- Dosing will be paused for any SAE that occurs in a participant receiving active treatment until causality is fully assessed by the PI and sponsor. Dosing may resume if the SAE is determined to be not drug-related by the PI and sponsor. If the SAE is determined to be either drug-related or unknown, either dosing will cease or the SAE will be evaluated by the sponsor's protocol review committee (or similar review group), which is independent of the study team and investigators. If the protocol review committee determines that dosing may resume, a plan that mitigates risks to participants with the resumption of dosing will be implemented. Such a plan could include a revision of inclusion/exclusion criteria, repeating or reducing the dose, or adding appropriate safety monitoring.
- It is determined that the limit of safety and/or tolerability has been reached. This
 decision will be made following discussions between the study team and the
 investigator.
- Other findings that, at the discretion of the study team and investigator, indicate that dose escalation should be halted.
- If, at any dose level, the average exposure reaches or exceeds the PK stopping limits:

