10.3.1. Definition of AE

AE Definition

- An AE is any untoward medical occurrence in a patient or clinical study participant, temporally associated with the use of study intervention, whether or not considered related to the study intervention.
- Note: An AE can therefore be any unfavorable and unintended sign (including an abnormal laboratory finding), symptom, or disease (new or exacerbated) temporally associated with the use of study intervention.

Events Meeting the AE Definition

- Any abnormal laboratory test results (hematology, clinical chemistry, or urinalysis) or other safety assessments (eg, ECG, radiological scans, vital sign measurements), including those that worsen from baseline, considered clinically significant in the medical and scientific judgment of the investigator. Any abnormal test results that meet any of the conditions below must be recorded as an AE:
 - Is associated with accompanying symptoms;
 - Requires additional diagnostic testing or medical/surgical intervention;
 - Leads to a change in study dosing (outside of any protocol-specified dose adjustments) or discontinuation from the study, significant additional concomitant drug treatment, or other therapy.
- Exacerbation of a chronic or intermittent preexisting condition, including an increase in either frequency and/or intensity of the condition.
- New condition detected or diagnosed after study intervention administration, even though it may have been present before the start of the study.
- Signs, symptoms, or the clinical sequelae of a suspected drug-drug interaction.
- Signs, symptoms, or the clinical sequelae of a suspected overdose of either study
 intervention or a concomitant medication. Overdose per se will not be reported as
 an AE or SAE unless it is an intentional overdose taken with possible
 suicidal/self-harming intent. Such overdoses should be reported regardless of
 sequelae.

Events NOT Meeting the AE Definition

- Any clinically significant abnormal laboratory findings or other abnormal safety
 assessments that are associated with the underlying disease, unless judged by the
 investigator to be more severe than expected for the participant's condition.
- The disease/disorder being studied or expected progression, signs, or symptoms
 of the disease/disorder being studied, unless more severe than expected for the
 participant's condition.
- Medical or surgical procedure (eg, endoscopy, appendectomy): the condition that leads to the procedure is the AE.

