- For each AE or SAE, the investigator must document in the medical notes that
 they have reviewed the AE or SAE and have provided an assessment of causality.
- There may be situations in which an SAE has occurred and the investigator has
 minimal information to include in the initial report to the sponsor. However, it is
 very important that the investigator always make an assessment of causality
 for every event before the initial transmission of the SAE data to the
 sponsor.
- The investigator may change their opinion of causality in light of follow-up information and send an SAE follow-up report with the updated causality assessment.
- The causality assessment is one of the criteria used when determining regulatory reporting requirements.
- If the investigator does not know whether or not the study intervention caused the event, then the event will be handled as "related to study intervention" for reporting purposes, as defined by the sponsor. In addition, if the investigator determines that an SAE is associated with study procedures, the investigator must record this causal relationship in the source documents and CRF, and report such an assessment in the dedicated section of the CT SAE Report Form and in accordance with the SAE reporting requirements.

Follow--up of AEs and SAEs

- The investigator is obligated to perform or arrange for the conduct of supplemental measurements and/or evaluations, as medically indicated or as requested by the sponsor, to elucidate the nature and/or causality of the AE or SAE as fully as possible. This may include additional laboratory tests or investigations, histopathological examinations, or consultation with other healthcare providers.
- If a participant dies during participation in the study or during a recognized follow-up period, the investigator will provide Pfizer Safety with a copy of any postmortem findings, including histopathology.

- New or updated information will be recorded in the originally submitted documents.
- The investigator will submit any updated SAE data to the sponsor within 24 hours of receipt of the information.

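### SAP 3.1.1 sets treatment emergence by event start alone, so worsening after a dose can be missing from the TEAE tables or appear under an earlier treatment

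*SAP*

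**What the plan says.** SAP 3.1.1 gives the basic rule: "An AE is considered a TEAE if the event started during the effective duration of treatment". It then sets the window, "All events that start on or after the first dose of study intervention" and before the end of the study, and closes the other side: "The algorithm will not consider any events that started prior to the first dose date". All three statements depend on the start of the event; none mentions a change in severity.

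The only sentence on attribution is: "Events that occur in a non-treatment period (eg, washout or follow-up) will be counted as treatment emergent and attributed to the most recent treatment taken". It covers events in washout or follow-up. It does not address an event that is already open when the next dose is given.

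SAP 6.1.1 calls for tables of TEAE incidence and severity by treatment, following sponsor reporting standards. It does not say which severity is shown when a grade changes. It also provides for AEs in general to be listed and summarized, apart from the TEAE tables.

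On the protocol side, section 8.4.1 starts AE collection at consent. Section 10.3.3 asks for one of three intensity categories per AE and, on follow-up, says: "New or updated information will be recorded in the originally submitted" documents. Section 10.3.1 includes among AEs: "Exacerbation of a chronic or intermittent preexisting condition, including an increase in" frequency or intensity.

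**The concern.** AEs by dose, population and dietary condition are part of the primary endpoint (SAP 3.1). In a crossover with ascending doses and placebo substitution, the by-treatment AE table is where a reader looks for a relation between dose and tolerability. A rule that looks only at event start loses the information that an existing event became worse after a given dose.

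Two situations are exposed. First, an event may begin between consent and Day 1 and worsen on drug. Second, an event may begin after one treatment, remain open when the next is given at least 7 days later, and worsen then. In the first, the worsening leaves the TEAE tables. In the second, nothing in the SAP directs it to the treatment it followed.

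**Working it through.** The plan states no figure to reproduce; the check is a reading of the rules followed by simple proportions.

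**Can such events exist?** Screening may take place up to 28 days before first dosing, and AEs are collected from consent, so pre-dose AEs can enter the database. Doses to one participant may be 7 days apart (protocol 4.1), so an AE can be open at the next dose. Protocol 7.1.4 foresees this for COVID-19, where dosing continues by default.

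**Case A: begins before first dose, worsens after it.**
- One record: the start precedes the first dose date, so the event is excluded from the TEAE tables under every treatment.
- New record opened at the worsening: the start is after dosing, so it is a TEAE under that dose.

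**Case B: begins mild after one treatment, becomes severe after the next.** For illustration, take two successive Cohort 1 dose levels with 8 active participants each (protocol 9.5), and assume that attribution follows event start.

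| Record and severity convention | Earlier treatment | Later treatment |
|---|---|---|
| One record, maximum severity | severe 1/8 | 0/8 |
| One record, initial severity | mild 1/8 | 0/8 |
| Split at the worsening | mild 1/8 | severe 1/8 |

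On a single record, the later treatment shows nothing under either convention. The choice of convention only decides whether the severe grade appears under the earlier treatment or nowhere.

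**Comparison within the SAP.** Sections 6.1.2, 6.1.3 and 6.1.5 each say how pre-dose findings from Period 2 onward are attributed across periods, for laboratory, vital-sign and ECG data. There is no counterpart for an AE that worsens across periods.

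**Weight of one participant in a column (1/n):**
- Cohort 1, 8 active: 1/8 = 12.5 points.
- Cohort 2, 6 active: 1/6 = 16.7 points.
- Cohort 3, 4 active: 1/4 = 25.0 points; at its maximum of 6 active, 1/6 = 16.7 points.
- A dose level given in Cohorts 1 and 2 and combined under SAP 5.2: 1/(8 + 6) = 7.1 points.

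**Opportunities in Cohort 1.** Planned dosings: 10 × 5 = 50. Dosings after an earlier one: 10 × 4 = 40. Of these, 2 × 4 = 8 are placebo, leaving 32 active. If Period 5 is the fed repeat of an earlier dose level, 8 × 3 = 24 active dosings remain in Periods 2 to 4. These count occasions on which Case B could arise, not expected errors.

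**The case against.** The case for leaving the text alone has real substance.

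- **Recording may solve it.** Protocol 10.3.1 counts exacerbation of a preexisting condition as an AE, so a site could open a new record with a post-dose start, and the SAP rule would then work. Protocol 10.1.7 refers to a separate document on CRF completion that may require this. This stands as a possibility. But the 10.3.1 wording concerns chronic or intermittent preexisting conditions and does not clearly cover an AE already open in the study, and 10.3.3 points to updating the original documents. The result then depends on site practice.
- **Sponsor standards may cover it.** They may fill the gap on severity and cross-period attribution. For pre-dose events, a worsening clause there would conflict with the SAP's explicit exclusion.
- **Few events.** Participants are healthy, doses are single, and escalation follows only a well-tolerated dose. This stands; the documents give no rate.

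Stronger readings are tempting but unsupported:

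- A reader might infer that the SAP charges an event at its worst grade to the lower dose. The SAP states neither a worst-grade rule nor an attribution rule for worsening across periods. That result requires a single record, attribution by start and maximum severity. The earlier treatment may also be placebo, or an equal or higher dose, so the direction of the shift is not fixed.
- A reader might infer that the severe-AE criterion in protocol 6.6.1, which counts events "in 2 participants at a given dose level", would be miscounted. That criterion is applied during the study by the study team and investigator on emerging data and does not use the SAP's TEAE algorithm.
- A reader might take 40 of 50 dosings as the size of the error. It is only a count of opportunities.

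**Conclusion.** The concern holds for the reported tables. Exclusion of a pre-dose event that worsens on drug follows from a stated rule, on the assumption that the event is kept on one record. Misplacement across periods is a gap: the SAP allows it but does not prescribe it, and it arises if the event stays on one record and is assigned by its start. The tabulated severity is undefined in either case.

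If one such event occurs, it moves a Cohort 1 active column by 12.5 points, with 16.7 and 25.0 points for columns of 6 and 4. How often this would happen cannot be derived from the documents. Pre-dose events are not lost altogether, since AEs are also listed. Escalation decisions are not shown to be affected. The change is still worth making, because it concerns the primary-endpoint tables and needs only wording.

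**What to change.** In SAP 3.1.1:

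1. Define a TEAE as an event that starts, or increases in severity, on or after the first dose, and limit the exclusion of pre-dose events to those that do not worsen after dosing.
2. Attribute an increase in severity after a later dose to that most recent treatment, at the new grade, with onset at the worsening.
3. In 6.1.1, state that maximum severity within treatment is tabulated.
4. While editing, use either first dose or first dose date throughout, so that an event starting on Day 1 before dosing has one clear classification.

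Align the CRF completion instruction so that a change in severity after a dose is captured with its date, for example by closing the line and opening a new one.

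The cost is a few sentences in the SAP and one CRF instruction; design, dosing and sample size are unchanged. The downside is a few more AE lines and, because SAP 6.1.1 also tabulates total numbers of events, a split event would count twice there. Counting incidence by participant, once per preferred term and treatment, avoids this in the incidence tables; a footnote can explain the event totals.
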